The analysis plan for each specific hypothesis is listed below. In addition to hypothesis testing to analyze effects of the intervention on sleep, PAP adherence, depressive symptoms and quality of life, we will develop models showing which covariates predict the values of each of the outcome measures. Prior to hypothesis testing, data will be cleaned, possible outliers identified, and data distributions evaluated for assumptions of analysis (e.g. normality, homogeneity of variance). If necessary, normalized rank transformations as described in Bonate²⁴ will be performed and normalized rank scores will be submitted to analysis.

Hypothesis 1: Compared to control participants, participants randomized to the intervention will have improved nighttime sleep (i.e., higher sleep efficiency, better self-reported sleep) and better PAP adherence (measured objectively) at 3-months follow-up.

This hypothesis tests for differences between the intervention and control groups in our primary outcome measures of nighttime sleep and PAP adherence, between baseline assessment and 3-months follow-up, which is our primary time endpoint. Subjective measures of sleep outcomes will include sleep diary (sleep onset latency, wake after sleep onset [WASO], and sleep efficiency) and sleep quality (PSQI). The objective measure of sleep outcome will be actigraphy (sleep efficiency), and the objective measure of PAP adherence will be downloaded from the PAP smart card (percent of nights with PAP use \geq 4 hours, and mean hours of PAP use per night). All outcomes will be assessed using intention to treat analyses. A 2 X 2 (time X group; where time = baseline or 3-month assessment; and group = intervention or control) analysis of covariance analysis will be used with Bonferroni-corrected post-hoc comparisons to investigate differences between the groups in terms of treatment effects in the sleep variables (where baseline and 3-month follow-up data will be available). For PAP adherence outcomes, there will be no “baseline” data (i.e., PAP adherence data isn’t available until the participant starts PAP therapy), so outcomes between groups will be compared with independent samples t-tests and Chi-square test for difference in proportions.

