We expect that the group by time analysis of covariance for the sleep variables will show a difference between groups, and post-hoc analyses will show increased nighttime sleep efficiency and improved self-reported sleep (indicated by lower PSQI scores) in the intervention group compared to the control group. Following review of graphical representation of our longitudinal results (on main outcome measures), we will use repeated measures ANCOVA models to test both linear and nonlinear (i.e., quadratic) differential changes over time. Post-hoc tests within each time point (using Tukey type 1 error control) will be conducted. We expect there will be no difference between intervention and control groups at baseline, but differences will be present at follow-up. Other participant characteristics will be considered as possible covariates to reduce bias in our estimate of treatment effects and to increase precision. The major covariates that we expect to consider are age, cognition (estimated by MMSE) and comorbidity (estimated by CIRS-G). Other covariates we will consider include specific diagnoses and medications that may interfere with sleep, and measures of the intervention process (DBAS-16 scores, Self-efficacy, Knowledge and Decisional Balance Index subscales).

Sample size calculations were performed for each of the main outcome variables using reported effect sizes and/or calculated effect sizes from reported sample means and standard deviations reported in the literature in prior studies of CBT-I for insomnia and behavioral PAP adherence interventions in outpatient adults (see Table 5). Prior literature indicates that CBT-I is an extremely potent intervention for insomnia, and the studies typically have large effect sizes and small samples. Some caution is warranted, however, since efficacy studies usually employ tightly controlled ‘ideal’ treatment conditions, which also yield larger effect sizes

than effectiveness studies with more ‘real world’ conditions. Regardless of these issues, even the most conservative estimates of effect size from the literature suggest we will have an adequate sample size to test our sleep outcomes. A recent meta-analysis of trials of PAP adherence interventions published as a Cochrane review was used in estimating sample size for the PAP adherence component of our intervention.^{Error! Bookmark not defined.} this analysis suggests we will have an adequate sample size to test our PAP adherence outcomes.

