For the proposed study, we calculated sample size based on the outcome at post-treatment, and either the reported effect size (d) or d calculated from the reported means and SDs. The table below lists sample size needs for the entire duration of the study (i.e., 6 months). Based on an expected 15% loss by six months, the 5th column in the table below projects the sample size needed for each of 2 groups at randomization to maintain sufficient sample size at 6 months to test the selected outcomes.

Table 5 lists expected effect size, shown as the variable “d” (difference between intervention and control groups at follow-up divided by standard deviation). For many outcomes, we list several expected effect sizes from the literature; references for these effect sizes are listed in the second column. The effect size estimates take into account expected change in controls over time, since we expect controls will change, but not as much as the intervention group. The sample size needed at randomization to detect effect size d is shown (column 4), followed by the number of enrolled participants needed for the 6-month analyses (column 5), taking into account expected dropout by this time point. Based on these calculations, 120 randomized participants (60 per group) will be adequate for analyses at both 3 and 6 months. In addition to these main analyses, we will perform follow-up subgroup analysis to identify two or three variables which identify participants who have the greatest positive response to the intervention. Testing for subgroups with better or worse response results in such a small sample that overfitting is a potential problem; this risk is discussed below.

For example, in Table 5 the third row (WASO by sleep diary) shows that to have the needed sample size (N=19 per group) completing the study (i.e., with follow-up assessment data) to test for an effect (based on an expected 15% participant loss by 6 months), we need to enroll 22 participants per group (column 5) at baseline to have 19 participants per group remaining at 6 months follow-up. For all variables listed, we expect an adequate sample size to test our hypotheses. For all sample size calculations, the dropouts are assumed not to change on average. All testing assumes a two-sided .05 significance level with 80% power.

Table 5: Sample size calculations

Outcome	Reference	Reported (or calculated) effect size d	Enroll per group for d: post-test	Enroll per group for d at 6 months
WASO				

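### Table 5: the d = .55 PAP adherence row asks for 62 per group at 6 months against 60 randomised, and eight of the nine sleep and depression sample sizes cannot be derived from the stated inputs

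*Combined protocol and SAP*

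**What the plan says.** The sample size text under Hypothesis 1 takes each effect size from the literature, as "either the reported effect size (d) or d calculated from the reported means and SDs", and defines d as "difference between intervention and control groups at follow-up divided by standard deviation". It adds: "All testing assumes a two-sided .05 significance level with 80% power". It also says that the effect sizes allow for change in controls, and that dropouts are taken to show no change on average. No analysis model or baseline-to-follow-up correlation is given for the sample sizes.

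Table 5 lists 13 rows, with the number per group at post-test (column 4) and the number to enrol for 6 months (column 5). The text concludes: "Based on these calculations, 120 randomized participants (60 per group) will be adequate for analyses at both 3 and 6 months", and again: "For all variables listed, we expect an adequate sample size to test our hypotheses". For PAP adherence it relies on a meta-analysis: "this analysis suggests we will have an adequate sample size to test our PAP adherence outcomes".

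The Sample size estimates section expects 15% loss by 6 months, leaving 51 per group. Hypothesis 1 plans a baseline-adjusted time-by-group analysis for the sleep outcomes. PAP use has no baseline, so those "outcomes between groups will be compared with independent samples t-tests and Chi-square test for difference in proportions".

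**The concern.** Table 5 is the plan's numerical support for N = 120. One PAP row exceeds the number randomised on the table's own figures, and PAP adherence is a primary outcome whose 6-month comparison is part of Hypothesis 3. In addition, most of the sleep and depression sizes are far smaller than the stated inputs give. Column 5 suggests that 12 to 32 per group would do for the sleep and depression outcomes, a margin that a reader cannot check. At stake is whether the adequacy statements can be relied on as written.

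**Working it through.** **Inputs.** d, two-sided .05 and 80% power from the sample size text and Table 5; 60 per group randomised; 60 × 0.85 = 51 completers per group at 6 months.

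**1. Rows that reproduce.** For a two-sample t-test, n per group is the smallest n at which the noncentral t (noncentrality d√(n/2), 2n − 2 degrees of freedom) gives 80% power. This is roughly 2(1.96 + 0.842)²/d² plus 1. For d = .59: 15.70/.3481 = 45.1; the exact solution is 46.1, so 47, as tabled. Likewise 1.12 gives 14 (table 14), .57 gives 50 (50), 1.37 gives 10 (10) and .55 gives 53 (54). This formula therefore fits the three PAP rows, the SF-36 row and one PSQI row, within 1.

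**2. Rows that do not.**

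| Row | d | Column 4 | n needed | Power at column 4 | n/0.85, rounded up |
|---|---|---|---|---|---|
| WASO, diary | .67 | 19 | 36 | 52% | 43 |
| Efficiency, diary | .68 | 13 | 35 | 38% | 42 |
| Efficiency, diary | .64 | 16 | 40 | 42% | 48 |
| Efficiency, actigraphy | .60 | 27 | 45 | 58% | 53 |
| Onset latency | .58 | 20 | 48 | 43% | 57 |
| Onset latency | .80 | 10 | 26 | 40% | 31 |
| PSQI | .58 | 20 | 48 | 43% | 57 |
| Depression | .67 | 14 | 36 | 40% | 43 |

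The inconsistency shows without any formula. The same d = .67 is given 19 in one row and 14 in another; d = .64 is given fewer (16) than the larger d = .67 for WASO (19); and .80 and 1.37 both get 10. If n depended only on d, alpha and power, none of this could happen.

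**3. Could baseline adjustment explain it?** ANCOVA multiplies n by (1 − r²), so r = √(1 − column 4/n). Actigraphy: √(1 − 27/45) = .63. Diary efficiency, d = .68: √(1 − 13/35) = .79. Allowing for small-sample t, the eight rows imply r of about .64 to .82. Six of them lie at .77 to .82, with WASO (.70 to .72) and actigraphy (.64 to .65) apart. A change-score calculation, with factor 2(1 − r), implies .70 to .84. By contrast, the SF-36 row implies an ANCOVA r of at most .08.

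**4. The d = .55 PAP row at 6 months.** Column 5 gives 62, above 60. Dividing by 0.85: 54/0.85 = 63.5, so 64; or 53/0.85 = 62.4, so 63. Power at 51 per group is 78.5%. The smallest d with 80% power at 51 is .560. The d = .59 row fits: 54 by the table, 47/0.85 = 55.3, so 56. Before any loss, 60 per group gives 84.8% for d = .55.

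**5. Other rows at 51 per group.** .57: 81.3%; .58: 82.7%; .59: 83.9%; .60: 85.1%; higher for the rest.

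**6. If dropouts are kept in.** Read literally, dropouts with no average change stay in the analysis and contribute no group difference. The effect is then about .85d on 60 per group (SD assumed unchanged). Power: .55, 72%; .57, 75%; .58, 76% (two rows); .59, 78%; .60, 79%. Six rows fall below 80%.

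**7. Column 5.** n/0.85 rounded up exceeds column 5 by 1 or 2 in nine of the 13 rows; with nearest rounding, five rows differ. The worked example ("we need to enroll 22 participants per group (column 5) at baseline to have 19 participants per group remaining at 6 months follow-up") has 19/0.85 = 22.35, which is 22 to the nearest integer and 23 rounded up.

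**The case against.** The best defence is that the sleep analysis is baseline-adjusted, so smaller sizes are to be expected. Six of the eight rows cluster at a similar implied correlation, possibly taken from the cited studies. The remarks on change in controls and in dropouts also point to a change-based calculation. This stands as far as it goes: a reader might infer that the eight sizes are arithmetic errors, and the documents do not prove that. But the correlation is not stated and no single value fits all eight rows, so the figures cannot be checked.

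On PAP, the plan lists several effect sizes per outcome and rests its conclusion on the meta-analysis row, which fits. The primary time point is 3 months, where the tabled 54 is below 60, and the 6-month shortfall in power is 1.5 points when completers are analysed. All this is fair and keeps the point small. It does not rescue a sentence that claims adequacy for every listed variable at both times, and PAP has no baseline value to adjust for.

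A reader might also infer poor power within AHI strata, should a block-by-group interaction prevent pooling. Table 5 claims nothing about strata and the documents give no split, so that argument is not made here. Nor is column 5 simply n × 1.15 throughout: 16 and 27 become 19 and 32, where that product gives 18.4 and 31.05. The one-unit differences there are partly rounding.

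**Conclusion.** Two faults stand. The adequacy sentences are untrue for the d = .55 PAP row at 6 months: 62 by the table, or 63 to 64 with division by 0.85, against 60. Eight of the nine sleep and depression sizes are underivable: the stated inputs give 1.7 to 2.7 times the tabled numbers.

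A reader might infer that the trial is too small. The documents do not support that for the sleep and depression outcomes: even with no gain from baseline data, those rows need at most 48 completers, or 57 randomised. At 51 completers per group, 12 of the 13 rows have at least 81% power and the remaining one has 78.5%. These figures assume the listed effect sizes, 15% loss and an analysis without dropouts. The plan's all-available-data analysis supports that last assumption, but the statement on dropouts allows the reading that gives 72% to 79% for the six rows with d of .55 to .60. The plan should say which applies. This should be fixed, as a fault in the justification rather than in the design.

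**What to change.** Keep N = 120.

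- **Column 4.** Either recompute every row with the two-sample formula that already fits the PAP and SF-36 rows (.67: 36, for both WASO and depression; .68: 35; .64: 40; .60: 45; .58: 48, both rows; .80: 26; 1.37: 10; .59: 47; .55: 53; 1.12: 14; .57: 50), or state the model and the correlation, with its source, for each row. The second option matches the planned sleep analysis more closely.
- **Column 5.** Compute it consistently as n/0.85, rounded up.
- **Adequacy sentences.** Qualify both: with 51 completers per group at 6 months, an unadjusted two-sample comparison has 80% power for d of about .56 or more, and 78.5% for the smallest PAP effect listed (d = .55).
- **Dropouts.** Reconcile that wording with the statement that dropouts do not change on average, and say whether the stated power leaves dropouts out or keeps them in with no group difference.

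The cost is a revised table and a few sentences, with no change to sample size, design or analysis. The plan would have to acknowledge power slightly below 80% for one of the three PAP rows at 6 months, or for six rows if dropouts are kept in.

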As described above, participants will be enrolled from the sleep clinics at VA GLAHS Sepulveda and West Los Angeles campuses. Based on FY11 data, at least 1037 patients per year will be diagnosed with OSA and prescribed PAP (using PAP equipment provided by VA GLAHS). We expect at least 52% will be aged ≥ 50 years, and at least 50% will also meet diagnostic criteria for insomnia. Based on this data, we conservatively estimate that at least 22 Veterans per month will be eligible for the study (i.e., [1037 PAP machines prescribed/12 months] \times [.52 aged ≥ 60 years] \times [.50 meet criteria for insomnia] =22.5). Based on consent rates in our prior VA studies we expect a 50% consent rate among eligible Veterans, which would provide at least 10 enrolled Veterans per month. We estimate that approximately 50% of enrolled participants

will meet all inclusion and exclusion criteria and be randomized, resulting in approximately 5 randomized participants per month, and our total target enrollment will be 120 randomized participants.

We have extensive experience in methods to encourage participant retention. For example, in our ongoing CBT-I trial in older Veterans, one of 122 participants who have reached the 6-month time-point has died, and only an additional 9 participants have been lost to follow-up due to other reasons, resulting in only 8.2% (10/122) loss by 6-months. In the current proposal, we conservatively estimate 15% loss by 6 months, which would result in approximately 102 (51 per group) participants completing the 6-month assessment. However, as in our prior work, we will monitor enrollment and participant loss throughout the study, to allow adjustment of the timeline and/or enrollment and retention procedures if we do not meet targets. As described in the analysis plan below, we will use standard “intention to treat” analysis, and sample size calculations have been made based on this analysis. Sample size calculations for each major outcome measure (described below) suggest that the target sample size will be sufficient to test our major hypotheses. All sample size calculations are based on 80% power and two-tailed P-value < .05.

Analysis Plan and Hypotheses

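### Table 5 does not use the stated assumption that dropouts do not change, so the basis of the 80% power is misstated, and on either basis 60 per group falls short for the PAP row with d = .55 at 6 months

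*Combined protocol and SAP*

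**What the plan says.** Under Sample size estimates, the plan adopts intention to treat and says that "sample size calculations have been made based on this analysis". The same section gives the error rates ("All sample size calculations are based on 80% power and two-tailed P-value < .05") and the expected loss: "we conservatively estimate 15% loss by 6 months, which would result in approximately 102 (51 per group) participants completing the 6-month assessment".

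The sample size text under Hypothesis 1 defines d as the "difference between intervention and control groups at follow-up divided by standard deviation". It says the effect sizes allow for change in controls and mentions no reduction for dropout. It then adds: "For all sample size calculations, the dropouts are assumed not to change on average". Its worked example enrols 22 per group so that 19 remain at 6 months, with d unchanged. It concludes: "Based on these calculations, 120 randomized participants (60 per group) will be adequate for analyses at both 3 and 6 months", and extends this to every variable in the table.

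Potential Shortcomings in the Proposed Analysis describes the analysis itself. Participants are compared by assigned group. Those who reject the intervention but still give data stay in. Where data stop, the plan uses all available data, repeats the analysis after EM estimation and reports both.

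**The concern.** The plan describes two different calculations. In an analysis of everyone randomised in which 15% of each arm show no change, the group difference shrinks to 0.85d, and the number randomised must rise by 1/0.85² = 1.38. Replacing dropouts leaves d intact and raises the number by only about 1.15 to 1.18. The text states the first and Table 5 does the second.

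A reader therefore cannot tell what the 80% refers to. This matters for PAP adherence, which is a primary outcome, and for quality of life, because those rows have little room at 60 per group.

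**Working it through.** **Inputs.** Two-sided alpha .05, 80% power, 60 per group and 15% loss by 6 months (51 per group left), from Sample size estimates and the text around Table 5. The d values and per-group numbers are from Table 5. The rows checked are SF-36 (.57), the PAP Cochrane review (.59) and the second PAP reference (.55).

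**Method.** Two-sample t-test with noncentrality d × √(n/2) and 2n − 2 degrees of freedom.

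**Step 1: reproduce column 4 at the full d.**
- d = .57: n = 49.3, so 50 (stated 50).
- d = .59: n = 46.1, so 47 (stated 47).
- d = .55: n = 52.9, so 53 (stated 54).

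**Step 2: reproduce column 5.**

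| d | Column 4 | × 1.15 | ÷ 0.85 | ÷ 0.85² | Stated column 5 |
|---|---|---|---|---|---|
| .57 | 50 | 57.5 | 58.8 | 69.2 | 58 |
| .59 | 47 | 54.05 | 55.3 | 65.1 | 54 |
| .55 | 54 | 62.1 | 63.5 | 74.7 | 62 |

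Column 5 is a single inflation for replacement. Nothing in it allows for diluted effects.

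**Step 3: power at 6 months on each basis.**

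| d | 0.85d | n per group for 80% at 0.85d | Power, 60 per group at 0.85d | Power, 51 per group at full d |
|---|---|---|---|---|
| .57 | .4845 | 68 | 74.9% | 81.3% |
| .59 | .5015 | 64 | 77.8% | 83.9% |
| .55 | .4675 | 73 | 71.9% | 78.5% |

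The third PAP row (d = 1.12) has over 99% power on either basis.

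**Step 4: smallest detectable effect at 80% power.** With 60 per group it is .516 among all randomised, which means a completer effect of .516/0.85 = .607 under no-change dropouts. With 51 per group at full d it is .560.

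**Step 5: sensitivity.**
- Loss that 60 per group can absorb under no-change dropouts, 1 − .516/d: 9.5% (d = .57), 12.6% (.59) and 6.2% (.55).
- Extra spread from mixing changed and unchanged participants lowers power by a little under one point by normal approximation: 75.6% to 74.8%, 78.4% to 77.5% and 72.6% to 71.8%.
- Baseline adjustment for quality of life, diluted effect, 60 per group: an assumed baseline correlation of .30 gives 78.8%, .35 gives 80.2% and .40 gives 81.9%.
- The plan gives no 3-month loss. If it were 7.5% (assumption), diluted power would be 81.7%, 84.3% and 78.9%.

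**The case against.** The strongest reply is that the diluted analysis will never be run. Intention to treat here means comparison by assigned group. The 15% is loss of follow-up data, not refusal of treatment, and no missing value is to be set to no change. Table 5 is compatible with that, and the SF-36 and PAP review rows then exceed 80%. This stands. A reader might infer from the no-change sentence that the trial misses its power for quality of life and for PAP generally; the documents do not support that.

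Three further points stand in part.
- **PAP.** There is no pre-treatment value, so no change is undefined; dilution there means assuming no group difference among dropouts. Usage is also sent daily by modem, so a missed visit need not mean missing PAP data. With all 60 per group at full d, the d = .55 row would have 84.8% power. But Table 5 itself applies the loss to PAP and asks for 62 per group.
- **Quality of life.** It is to be analysed by covariance analysis, so a moderate baseline correlation could recover the diluted shortfall. Table 5 takes no credit for this in the SF-36 row, and PAP has no baseline from which to gain.
- **Timing.** The primary time point is 3 months and the 15% belongs to 6 months, so no 3-month shortfall can be shown.

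A reader might also set the detectable effect of .61 against every d in Table 5 and call each smaller one underpowered. Three of those (.60, .58, .58) are sleep rows whose stated numbers (27, 20, 20) do not follow from d by a two-sample t-test, which needs 45, 48 and 48. The dilution argument cannot be carried over to rows whose method is unknown.

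**Conclusion.** The inconsistency is certain. The no-change assumption enters no figure in Table 5 and does not match the planned missing-data analyses.

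Its size depends on which statement is kept. If the assumption is kept, 6-month power by unadjusted t-test is about 75%, 78% and 72% rather than 80%; the PAP review row misses narrowly (64 needed, 60 planned). If the available-data analysis is the basis, only the d = .55 row misses, at about 79%. It misses on Table 5's own terms too, 62 against 60, so the blanket adequacy claim is not correct.

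These figures assume 15% loss in each arm, the Table 5 effect sizes and, for dilution, no group difference among dropouts. The point is one of stated basis and modest power. It does not show that the design, the sample size or the intention-to-treat analysis is wrong.

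**What to change.** Keep N = 120 and the analysis by assigned group, and state one basis for the power.

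- **Preferred:** delete the no-change sentence. State that Table 5 is an available-data calculation with about 51 per group at 6 months and a detectable d of about .56. State that the d = .55 PAP row has about 79% power, and limit the adequacy claim accordingly.
- **Alternative:** if the no-change assumption is retained, restate 6-month power as about 75% (SF-36), 78% (PAP, d = .59) and 72% (PAP, d = .55), with a detectable completer d of about .61. Say what no change means for PAP.

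Either way, give the loss expected at 3 months, since that is the primary time point. The cost is a few sentences and slightly less favourable stated power; no participants or procedures are added.
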